1.2 Secondary Objectives

- Quantify changes in strength, and body composition, before and following supplementation
- Determine feasibility of beetroot supplementation in head and neck cancer patients defined for each patient as the proportion of days successfully consumed supplement during treatment schedule
- Determine the toxicity of concentrated beetroot given in conjunction with radiation or chemo-radiation in SCCHN as measured by CTCAE v. 4.0
- Evaluate the trend in grade of mucositis during radiotherapy or chemoradiotherapy as measured weekly by CTCAE v 4.0
- Determine 1- and 2-year locoregional control rate and progression-free survival of subjects enrolled on this clinical trial.

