5. TREATMENT PLAN

This is a non-randomized, pilot Phase II clinical trial that will determine the safety of concentrated beet root given in conjunction with radiation or radiation plus chemotherapy for locally advanced head and neck cancer. This trial will enroll 25 subjects taking beetroot supplement with up to an additional 10 standard of care subjects that refuse participation in the beetroot supplementation but are willing to obtain strength outcomes during their cancer treatment for a maximum of 35 patients.

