10.2 Calendar for Beetroot Supplementation Cohort

Timepoints	Baseline	Weekly during Concurrent Radiation and Cisplatin	Midpoint (After IMRT)	Endpoint (4-6 weeks following Midpoint testing)	Off-treatment	Off study
Studies:						
H&P ¹ VS	X	X	X	X	X	X
TOX	X	X	X	X		
Pregnancy Testing	X					
Muscle Strength and Endurance Testing	X		X	X		
Body Composition (DXA)	X		X	X		
Plasma/Salivary Nitrate/Nitrite	X		X	X		
QOL and Mucositis	X		X	X		
Diet	X		X			
Ct SCAN (body comp)	X		X	X		
Routine Cancer Imaging ²	X			X		X
Treatments:						
Beet Root (daily) ³	X	X	X	X		

1) Abbreviations: H&P=History and Physical examination; PS=ECOG performance status; VS=vital signs (blood pressure, temperature, pulse and respiratory rates, weight and height); TOX=toxicity assessment

2) Routine cancer imaging will be standard of care CT or MRI scans to document disease and response to therapy. These will be required pre-treatment, post-chemoradiation and at 1- and 2-year follow-up (+/- 6 weeks), as per standard of care.

3)Beet root will be self-administered each day (M-F in afternoon)

4)Toxicity will be followed for all patients until (endpoint) testing. Any beetroot related toxicity $>$ grade 2 will be followed until resolution to grade 1 or less.

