11.2.6 Progression-Free Survival

Progression-free survival (PFS) is defined as the duration of time from start of treatment to time of progression or death, whichever occurs first.

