13.3 Data Analysis

Following study completion, primary data analysis will include estimation of subjects achieving treatment compliance along with corresponding exact 90% binomial confidence intervals.

Other secondary endpoints listed in section 13.1 will be primarily descriptive as they are exploratory in nature; however means and standard deviations (or N and percentages where appropriate) will be estimated and summarized for each time point to gain more information of expected effect size differences between standard therapy and BR arms. Repeated measures ANOVA will be utilized to test for exploratory differences in these various measures over time points between BR and standard therapy arms. Kaplan-Meier curves will be presented for locoregional control and progression-free survival along with 90% confidence interval bounds. Exploratory log rank tests will be performed to assess for any preliminary differences in these survival outcomes by treatment arm.

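### Locoregional control is assigned to Kaplan-Meier with no event definition and no rule for death; if deaths without locoregional failure are censored, the failure rate is overstated

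*Combined protocol and SAP*

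**What the plan says.** Section 1.2 lists as a secondary objective: "Determine 1- and 2-year locoregional control rate and progression-free survival of subjects enrolled on this clinical trial". Section 13.1 repeats locoregional control among the outcomes for which pilot estimates are wanted.

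The method is in section 13.3: "Kaplan-Meier curves will be presented for locoregional control and progression-free survival along with 90% confidence interval bounds". It continues: "Exploratory log rank tests will be performed to assess for any preliminary differences in these survival outcomes by treatment arm". The same section says that the secondary endpoints "will be primarily descriptive as they are exploratory in nature".

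For PFS, section 11.2.6 gives the definition: "the duration of time from start of treatment to time of progression or death, whichever occurs first". There is no counterpart for locoregional control anywhere in the document, and no competing-risk or cumulative-incidence method is mentioned.

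On size, section 5 states: "This trial will enroll 25 subjects taking beetroot supplement", with up to 10 further observational subjects. The beetroot calendar (section 10.2) requires disease imaging before treatment, "post-chemoradiation and at 1- and 2-year follow-up (+/- 6 weeks), as per standard of care".

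**The concern.** Kaplan-Meier suits PFS because death is part of the event. Locoregional control, in its ordinary sense, means absence of local or regional failure, and a death from distant disease, another cancer or comorbidity is not such a failure. If a death is not an event, a plain Kaplan-Meier analysis censors it. Censoring assumes that the patient could still fail locoregionally later, at the same rate as those who remain under observation. The curve then describes a setting in which nobody dies first, not the proportion of enrolled patients who fail by 1 or 2 years.

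Such deaths are foreseeable. Sections 3.1.1 to 3.1.5 admit patients with a prior malignancy, ECOG status up to 2 and a life expectancy only a little over 3 months. At stake are the 1- and 2-year rates that the pilot would pass on to a later study. Adding patients does not reduce this bias, and the confidence interval does not reflect it.

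**Working it through.** **Plan's own figure.** There is none on this point: the documents state no locoregional rate, death rate or event count. The only precision figure for 25 patients is the compliance half-width of 17.7% in section 13.2. It reproduces as the maximum exact (Clopper-Pearson) 90% half-width, 17.67%, and serves here only as a sense of scale.

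**Direction.** Let hL be the hazard of locoregional failure and hD the hazard of death without it. With deaths censored, one minus Kaplan-Meier targets the integral of hL(u)·exp(−HL(u)), where H denotes a cumulative hazard. The actual probability of failure is the integral of hL(u)·exp(−HL(u) − HD(u)). Since exp(−HD) is at most 1, the first is never below the second. They are equal if no competing deaths occur.

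**Size with constant hazards (assumed).**
- 1−KM(t) = 1 − exp(−hL·t)
- Cumulative incidence(t) = hL/(hL+hD) × [1 − exp(−(hL+hD)·t)]

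For hL = hD = 0.15 and t = 2: 1 − exp(−0.30) = 25.9%, against 0.5 × [1 − exp(−0.60)] = 22.6%.

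| Annual hazards, each | 2 years: 1−KM | 2 years: cumulative incidence | Gap at 2 years | Gap at 1 year |
|---|---|---|---|---|
| 0.10 | 18.1% | 16.5% | 1.6 points | 0.5 points |
| 0.15 | 25.9% | 22.6% | 3.4 points | 1.0 points |
| 0.20 | 33.0% | 27.5% | 5.4 points | 1.6 points |

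**Sensitivity to the equal-hazards assumption.** Fix instead the true 2-year probabilities L (locoregional failure) and D (death without it). Then hL + hD = −ln(1−L−D)/2 and hL = (hL+hD)·L/(L+D).

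| L / D at 2 years | 1−KM at 2 years | Gap |
|---|---|---|
| 10% / 5% | 10.3% | 0.3 points |
| 20% / 10% | 21.2% | 1.2 points |
| 30% / 10% | 31.8% | 1.8 points |
| 30% / 20% | 34.0% | 4.0 points |
| 40% / 30% | 49.7% | 9.7 points |

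**Against sampling error.** In 20,000 simulated cohorts of 25 patients with a 2-year horizon:
- With 30%/10%, mean 1−KM was 31.9% and mean Aalen-Johansen 30.0%, with approximate 90% half-widths of 15 to 16 points.
- With 30%/20%, the means were 34.1% and 30.1%, with half-widths of 15 to 17 points.

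**The case against.** The strongest objection is that the documents nowhere say that deaths will be censored. Locoregional control is simply undefined. If death were counted as an event, the Kaplan-Meier curve would estimate locoregional-failure-free survival and this bias would not arise. That stands. A reader might infer from section 13.3 that the plan censors deaths and that its rates will therefore be wrong; the text supports only the conditional statement. Counting death would not close the gap, however, because the result would be a different quantity under the name of locoregional control.

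Second, the size rests on assumed hazards. Setting the competing-death hazard equal to the failure hazard implies that 16.5% to 27.5% die without locoregional failure by 2 years, which may be too high when distant metastases are excluded at entry. With fewer such deaths the gap is 1 to 2 points or less. This also stands, as does the comparison with a half-width of roughly 15 points.

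Third, a reader might infer that the log-rank test is invalid. It is not. With deaths censored it compares cause-specific hazards, which is a legitimate target; Gray's test addresses a different one. The comparison is in any case exploratory, non-randomised, and 25 against at most 10, and the observational calendar in section 10.3 lists no cancer imaging.

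**Conclusion.** The point holds in conditional form. The endpoint lacks an event definition, a time origin and a rule for death, and the only estimator named is one that overstates failure if deaths are censored. Under equal annual hazards of 0.10 to 0.20 the overstatement is about 1.6 to 5.4 points at 2 years and 0.5 to 1.6 points at 1 year. Other assumed mixes give 0.3 to 9.7 points at 2 years, and it is zero without competing deaths. None of these inputs comes from the documents.

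The effect lies within the sampling error of a 25-patient cohort and concerns a secondary, descriptive endpoint. The primary compliance analysis, the sample size and the interim review are untouched. The documents do not support a claim that the reported rates are certain to be biased, or that the cohort comparison fails for this reason. The change is worth making because it is cheap and makes the reported rate interpretable.

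**What to change.** Add a definition of locoregional control beside section 11.2.6: what counts as locoregional failure, the time origin (for example the same as for PFS), the censoring rule, and the handling of death without locoregional failure.

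In section 13.3, replace Kaplan-Meier for this endpoint with the Aalen-Johansen cumulative incidence of locoregional failure at 1 and 2 years with 90% confidence intervals, treating death without locoregional failure as a competing event. Keep Kaplan-Meier for PFS. The Kaplan-Meier curve for locoregional control may be shown alongside for comparison with historical series. If death is meant to be an event, name the endpoint locoregional-failure-free survival and keep Kaplan-Meier.

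The exploratory log-rank test may stay if it is described as a comparison of cause-specific hazards; Gray's test is optional.

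The cost is a few sentences and standard software. No new data are needed beyond what PFS and the planned imaging already require, and neither sample size nor conduct changes. The drawback is that the reported rates may differ by a few points from historical Kaplan-Meier figures.

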13.4 Reporting and Exclusions

13.4.1 Evaluation of Toxicity

All subjects on beet root supplementation will be included in the safety analysis, with toxicities graded according to NCI CTCAE v4.0. Incidence tables will be generated to summarize incidence of patients reporting at least one episode of each specific adverse event, incidence of adverse events causing withdrawals and incidence of serious adverse events. Listing of adverse events by patients will include the time to onset, the duration of each event, the severity of each event, and the relationship of the event to study therapy, whether it was a serious event, and whether it caused withdrawal. This will also capture all incidence and severity of mucositis during the duration of this study.

13.4.2 Evaluation of Outcomes

All patients included in the study will be assessed for treatment compliance, even if there are major protocol treatment deviations or if they are ineligible. All of the patients who met the eligibility criteria (with the possible exception of those who received no study medication) will be included in the intent to treat analysis for the primary completion endpoint as well as all secondary outcomes.

Due to concerns of potential non-compliance of taking all beet supplements over the course of primary treatment, a per protocol analysis will also be performed for all patients that consume at least 3 servings of the required beet supplements per week. Percentage of beet supplements taken will also be reported as part of this subgroup analysis.

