1. OBJECTIVES

1.1 Primary Objectives

Obtain preliminary data estimates of treatment compliance of radiation alone or chemoradiation (as defined by completion of initially prescribed radiotherapy and chemotherapy) in patients receiving beetroot (dietary nitrate/nitrite supplementation) and treatment for head and neck cancer

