13.2 Sample Size/Accrual Rate

The primary endpoint of this study is treatment compliance, for the chemoradiation strata defined as completion of radiotherapy and 3 cycles of chemotherapy with no treatment delay with published historical rates average around 52.1% (30). For those receiving radiation alone, we predict higher compliance rates closer to 70% as these patients tend to experience less mucositis and adverse events during treatment. We anticipate 60% of patients will receive radiation alone versus 40% receiving chemoradiation. 25 total patients (10 – chemoradiation, 15 – radiation alone) receiving beet root supplementation, will result in 90% confidence intervals around each estimated compliance rate with a maximum widths of +/- 27.75% and 22.85% for chemoradiation and radiation alone respectively. The combined estimate of compliance will still have a 90% confidence interval estimate with a maximum width of +/- 17.7% as previously designed. For the 10 subjects in the observational cohort not receiving beet root supplementation, we will still be able to estimate compliance rates +/- 27.75% and obtain pilot data regarding strength outcomes during standard of care therapy. This design is not powered to compare compliance rates between treatment strata or beet root versus standard of care; instead it allows us to gain preliminary information about these rates with a certain amount of precision as pilot data for a larger, more definitive study. We plan to accrue patients over a 2 year period.

There will be a pre-specified safety consideration after half of the planned enrollment in the beet root supplementation (interim after 13) to verify acceptable treatment completion rates as compared to a published historical rate of 52.1%. Two prior beta distributions (non-informative and null-hypothesis based) will be considered with patient information collected from the first 13 enrolled in beet root arm to calculate the posterior probability that the mean proportion of successful completion is less than or equal to historical rates of 52.17% with corresponding 90% credible intervals. The study team will reconsider continuation of the protocol due to safety and feasibility concerns if either arm has a high probability of experiencing a success rate lower than published rates.

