13.5 Data Management

All cancer treatment related data, adverse events, and compliance with BR supplementation will be stored in the OnCore Data Management System of the Markey Cancer Center, as well as all strength measurements, body composition (CT and DXA), and quality of life surveys. Case report forms will record all study endpoints and data will be accessed in a secure manner using this password protected, encrypted software. The study statistician, along with staff from the Biostatistics Shared Resource Facility (BSRF), will work closely with the study PI and the MCC CRO staff on the development of eCRFs for the study. Instructions for data entry will be listed in Study-Specific Data Management Plan created by CRO staff in conjunction with the study statistician. The OnCore database is housed on secure servers maintained by the Cancer Research Informatics Shared Resource Facility (CRISRF) of Markey Cancer Center. The database is backed up daily.

Each subject will be assigned a sequence number at time of study entry through the OnCore system. This same sequence number will be distributed to study personnel at CCTS and utilized for all data. Data will be accessed by the study statistician via OnCore on a regularly scheduled basis to perform statistical programming to assess data quality control, study recruitment and to generate interim reports and analyses. In collaboration with the study team, procedures and timelines will be developed for data quality control, resolution of data queries, interim reporting and final data analysis.

REFERENCES

1. Society AC. Cancer Facts & Figures 2012.

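### Does section 13.4.2 leave the denominator of the primary compliance rate open?

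*Combined protocol and SAP*

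**What the plan says.** Section 13.4.2 has two consecutive sentences on the primary endpoint. The first says that all included patients are assessed for treatment compliance, "even if there are major protocol treatment deviations or if they are ineligible". The second sentence is narrower and is about "All of the patients who met the eligibility criteria (with the possible exception of those who received no study medication". Of this smaller group the plan states that they "will be included in the intent to treat analysis for the primary completion endpoint", and the same set serves for every secondary outcome.

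Section 13.3 names the estimator, "estimation of subjects achieving treatment compliance along with corresponding exact 90% binomial confidence intervals", but no analysis set. Section 13.2 plans for 25 patients receiving the supplement (10 chemoradiation, 15 radiation alone) and states a combined "90% confidence interval estimate with a maximum width of +/- 17.7" percent. Other sections also describe the target group by exposure. Section 1.1 sets the objective "in patients receiving beetroot (dietary nitrate/nitrite supplementation) and treatment for head and neck cancer", and section 5 says "This trial will enroll 25 subjects taking beetroot supplement".

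On data access, section 13.5 says "Data will be accessed by the study statistician via OnCore on a regularly scheduled basis". Section 13.2 has a review of completion after the first 13 patients enrolled in the beetroot arm.

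**The concern.** Treatment compliance is the primary endpoint, so a sentence that includes ineligible patients, followed by one that restricts the analysis to eligible patients, looks like two rules for one rate. The bracket on never-dosed patients is not a rule either: it allows an exclusion without saying who decides, when, or on what ground. An eligible-only set is also not what most readers understand by intent to treat.

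The trial is open and non-randomised, completion is looked at after 13 patients, and the statistician sees the data regularly. In principle the exception could be settled with outcomes known. The compliance rate is the main product of the pilot and is meant to inform a larger study. Each patient is worth 1/25 = 4 points overall and 1/10 = 10 points in the chemoradiation stratum.

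**Working it through.** **1. The plan's own precision.** The inputs are n = 10, 15 and 25 and the 90% level (13.2), with exact binomial limits (13.3). For x compliant out of n, the lower limit is the 0.05 quantile of Beta(x, n − x + 1) and the upper limit is the 0.95 quantile of Beta(x + 1, n − x). The largest half-width over all x is:

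| n | Stated in 13.2 | Exact, recomputed |
|---|---|---|
| 10 | 27.75 | 27.76 |
| 15 | 22.85 | 22.81 |
| 25 | 17.7 | 17.67 |

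The stated figures reproduce to within 0.04 points. A normal approximation at 50% gives 26.0, 21.2 and 16.4 and does not match. The sample-size statement is sound.

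**2. An expected result.** From the rates in 13.2, 10 × 0.521 + 15 × 0.70 = 5.21 + 10.50 = 15.71, or about 16 of 25, taken as 5/10 plus 11/15. The rate is 16/25 = 64.0% (exact 90% CI 45.6 to 79.8).

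**3. One patient left out.** The documents give no count of ineligible or never-dosed patients, so one is an assumption.

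| Set | All counted | One compliant patient out | One non-compliant patient out |
|---|---|---|---|
| Combined | 16/25 = 64.0% | 15/24 = 62.5% (43.7 to 78.8) | 16/24 = 66.7% (47.9 to 82.2) |
| Chemoradiation | 5/10 = 50.0% | 4/9 = 44.4% | 5/9 = 55.6% |
| Radiation alone | 11/15 = 73.3% | 10/14 = 71.4% | 11/14 = 78.6% |

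The combined rate moves by 62.5 − 64.0 = −1.5 or 66.7 − 64.0 = +2.7 points. The chemoradiation rate moves by 5.6 points either way, against a planned half-width of 27.75.

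**4. Precision with fewer patients.** The maximum half-width is 17.67 at n = 25, 18.06 at n = 24 and 18.44 at n = 23. Losing one patient costs 18.06 − 17.67 = 0.39 points. Sections 5 and 13.2 count the 25 as patients taking or receiving the supplement, so a dosed-only set can itself be 25 and the stated 17.7 then stands.

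**5. How often the exception could apply.** Patients who decline the supplement enter the observational cohort under a separate consent and registration (5.1.4). In the beetroot cohort, staff supervise the first self-administration, and dosing starts on the day the supplement is handed over (5.1.3). A patient registered to beetroot who never takes a dose should be rare.

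**The case for a change.** The strongest case for a change is that the first sentence may only describe data collection, but even so the fate of never-dosed patients is undecided and the set is mislabelled. Both points are true. Read literally, the clause on receiving no study medication would also cover the whole observational cohort, for which 13.2 plans a compliance estimate. No analyst would apply it that way, though the wording is loose. Section 5.3 also takes patients off study if they complete less than half of planned therapy, and 13.4.2 does not say outright that they stay in the denominator. They fail the compliance definition in 5.1.5, so the natural reading keeps them as non-compliant.

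A larger effect can be constructed. If three patients were left out and all had the same outcome, the rate would run from 13/22 = 59.1% (39.5 to 76.7) to 16/22 = 72.7% (53.2 to 87.4). Nothing in the documents supports three exclusions, let alone three that all point the same way.

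The worry about choosing the rule late carries limited weight. Eligibility and a first dose are facts that date from before or at the start of a course of about seven weeks, although an eligibility failure may come to light later. They cannot be reclassified to suit the outcome; only the choice of rule is open. The look after 13 is already tied to enrolment. Because every included patient is assessed, the all-patient rate can always be shown beside the restricted one.

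A side point concerns the per-protocol set. Sections 5.1.3 and 13.4.2 use the same threshold of three servings in a week, and 5.1.3 adds the period. A full week withheld under section 6 leaves 0 weekday doses plus at most 2 weekend make-up doses, so fewer than 3, if make-up applies at all. This affects only a supportive analysis whose purpose is to set aside under-exposed patients.

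**Conclusion.** The plan can stand. Section 13.4.2 names the set for the primary analysis. The gap is whether a rare never-dosed patient is counted, together with an intent-to-treat label on an eligible-only set. Counting all enrolled patients keeps to the enrolled group. Counting only dosed patients fits an objective written for people receiving beetroot. Each gives a valid descriptive rate with an exact interval, and choosing between them is a fair trade-off.

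On the assumption of one affected patient and about 16 of 25 compliant, the difference is 1.5 to 2.7 points against a half-width of about 17.7. Section 13.2 says that the design is not powered to compare compliance rates, and 13.3 plans no test of the final rate. A sensible analyst would state the denominator used, keep non-completers as non-compliant, and give the other rate alongside. The conclusion would weaken only if several patients proved ineligible or never dosed and shared one outcome, which the documents give no reason to expect.
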